The overuse of medications with psychoactive properties such as antipsychotics, benzodiazepines, or sedative hypnotic “Z-drugs”, is extremely common in inpatient and acute care settings to manage delirium and agitation, despite the considerable risks associated with their use and guidelines that recommend their avoidance in older adults.¹⁻⁴ In addition to their short-term risks, many patients are discharged on these potentially inappropriate medications which leads to longer-term adverse consequences such as falls and cognitive decline.^{5,6} While there are many contributors to the prescribing of these high-risk medications in the inpatient setting, provider-level barriers are thought to be central. These include clinical inertia (i.e., habits/culture of prescribing), perceived pressure from front-line nursing staff or patients and/or their caregivers, a lack of familiarity with a particular patient and fatigue.⁷⁻⁹

Unfortunately, efforts to address these barriers have been largely unsuccessful.¹⁰⁻¹³ We hypothesize that this reflects inadequate addressing of the specific needs of complex and acutely-ill inpatients in stressful clinical situations by providers.

In stressful situations, people rely on automatic, quick, or even emotional thinking, sometimes referred to as “System 1” thinking and may make different decisions than they would if they were instead using controlled, slow or rational or “System 2” thought.¹⁴⁻¹⁷ One example of a behavioral principle describing these differences is the “hot-cold” empathy gap which is based on the observation that when people are in rational or “cold” states, they incorrectly predict what their behavior will be during “hot states”.¹⁸ Other related behavioral principles include those that describe deliberative versus impulsive thinking and have found similar gaps in behaviors when people are in different states.¹⁹⁻²¹

In the case of health care, the “empathy gap” has been thought to lead physicians to underestimate their actual prescribing of antibiotics or opioids when experiencing pressure to do so.¹⁷ For the prescribing of potentially-inappropriate medications to acutely-ill inpatients, most interventions have focused on educating and training providers when they can access System 2 thinking mechanisms, and may not have adequately prepared them for making complex and urgent therapeutic decisions under System 1 conditions.^{14,22}

Efforts to address decisional gaps between System 1 and System 2 thinking in other fields have involved role-playing or games to simulate System 2 thinking states, such as having participants

evaluate their cravings for tobacco during hot state and cold state sessions.^{14,15,23,24} In clinical medicine, simulation has increasingly been used to help health care professionals, alone and in teams, practice how they would handle stressful situations such as cardiac arrest or emergent trauma situations in emergency rooms.²⁵⁻³¹ By extension, these approaches could help address decisional gaps for prescribing high-risk medications for older adults, thereby improving patient safety and welfare.

2. Study Aims

We propose a 2-phase project consisting of provider qualitative interviews and a 2-arm pilot randomized controlled pragmatic trial in which physicians in training (interns) caring for elderly inpatients are assigned to receive simulation training or an educational control. The main goal of this project is to improve patient safety.

The objectives and endpoints for the trial are summarized below.

OBJECTIVES	ENDPOINTS	JUSTIFICATION FOR ENDPOINTS
Primary		
To determine whether simulation-based training reduces the prescribing of high-risk medications to hospitalized older adults.	Number of high-risk medications doses prescribed per day to eligible patients assigned to intervention providers compared with control providers.	This outcome is measurable using electronic health record (EHR) data and will provide evidence of provider behavior change during the follow-up period.
Secondary		
To evaluate whether simulation-based training reduces the continued prescription for high-risk medication to hospitalized older adults at discharge.	Discharge medication order written for one of the eligible high-risk medications to eligible patients assigned to intervention providers versus control providers	This outcome is measurable using EHR data and will provide evidence of whether the intervention results in fewer high-risk medications for patients at discharge.
To determine whether there are impacts of simulation-based training on prescribing of other related medications.	Number of medication doses prescribed per day to eligible patients assigned to intervention providers versus control providers for opioids, trazodone, and melatonin	This outcome is measurable using EHR data and will provide evidence of whether there are spillover effects on other related medications.

OBJECTIVES	ENDPOINTS	JUSTIFICATION FOR ENDPOINTS
To evaluate adoption and implementation outcomes for the intervention	Implementation outcomes informed by the Reach Effectiveness Adoption Implementation Maintenance (RE-AIM) framework: 
• Characteristics of consenting and non-consenting providers• Completion of the simulation training (intervention) or online educational training (control)• Feedback from and issues reported by providers about the intervention• Self-reported satisfaction with the intervention	These outcomes capture the extent to which the intervention could be replicated on a larger scale. This approach will provide valuable information regardless of the results of the trial, as evaluating implementation will enable us to explain why the intervention did not work, should that turn out to be the case. These outcomes are also easily measurable using baseline and endline (follow-up) questionnaires.

3. Study Design

3.1 Study site

Study participants will be providers recruited from the general medicine inpatient service at Brigham and Women's Hospital (BWH) and Brigham and Women's Faulkner Hospital (BWFH). BWH is part of Mass General Brigham (MGB), formerly known as Partners Healthcare, a large hospital system in Boston, MA, and are both staffed by the same general medicine service at the main BWH campus.

3.2 Overall design

We propose a 2-phase project consisting of provider qualitative interviews and a 2-arm pilot randomized controlled pragmatic trial in which physicians in training (interns) caring for elderly inpatients are assigned to receive simulation training or an educational control.

The first phase, qualitative interviews, are a separate aim from the pragmatic trial and have already been reviewed and approved by the MGB IRB and is governed under a separate protocol (MGB IRB: 2020P002467). This aim consists of brief virtual qualitative interviews with approximately 25 inpatient providers and allied team members (e.g., nurses or pharmacists) to elicit perspectives on prescribing of high-risk medications in the in-patients setting as well as simulation-based training. These interviews are being conducted virtually with providers at other MGB sites and former interns who are no longer part of the general medicine service to avoid contamination with the trial using an MGB-approved video platform. This aim is being used to inform the design of the simulation-based training intervention used

in Aim 2 (pragmatic trial). Providers are identified through referrals by clinicians and recent prescribing history and contacted through email invitation. They are providing verbal consent for their participation and receiving renumeration for their participation. **The remainder of this protocol is about the 2-arm pilot randomized trial.**

The 2-arm pilot randomized controlled trial will determine whether a newly-designed simulation-based training program for providers based on underlying principles of System 1 and System 2 thinking reduces prescribing of high-risk medications for hospitalized older adults versus control, with the ultimate goal of improving patient safety. We will also measure subsequent prescribing for patients cared for by other providers and other adoption and implementation outcomes to explore the extent to which the intervention could be used at scale.

BWH and BWFH uses 2-week service blocks for its inpatient general medicine evening coverage, and the service overall consists of 6 day and 8 evening (twilight) teams covering geographically distinct wards at 2 hospital sites with daily censuses of 15-20 patients. These teams typically consist of an attending, a resident, an intern (i.e., 1st year of residency), and medical students. There is no cross-coverage across teams. We will focus on interns from the “twilight” (i.e., evening) teams as they cover the shifts during which the high-risk medications of interest (specifically anti-psychotics, benzodiazepines, and sedative hypnotic “Z-drugs”) are typically first initiated and are also the first point of contact for nurses, pharmacists, and other physicians. Given their stage of training and the nature of their workflow, they are also most prone to make decisions using System 1 thinking.

At the beginning of each rotation, we will identify the interns assigned to the twilight teams (i.e., the primary prescriber and responding clinician on the general medicine service team). We will invite these interns to participate in the study via email invitation. Interns who consent will be randomized in a 1:1 ratio with a random number generator to one of 2 arms: (a) Arm 1: simulation intervention and (b) Arm 2: control (online education) intervention. The unit of randomization will therefore be the intern. Randomizing at the intern level will reduce the possibility of contamination across patients. Providers will receive \$25 for completing the initial provider survey, \$75 for completing the intervention or control assignment (e.g., simulation or online education training), and \$50 for completing the endline (follow-up) questionnaire. Other ward staff will be blinded to arm assignment to the extent possible. Data analysts will be blinded to arm assignment. This is a highly feasible approach used by investigators conducting provider-facing intervention trials at BWH.

[figure not shown]
Providers assigned to the intervention arm will participate in a short simulation training at the beginning of their 2-week block (planned for their second day). The training will take place at the Neil and Elise Wallace STRATUS Center for Medical Simulation at Brigham and Women's Hospital and will follow all of their recommended and hospital-recommended practices on social distancing, including the learning limits. The training will also be led by [name], hospitalist, Instructor in Medicine, and Assistant Director for Medicine at STRATUS. Based on discussion with [name], the study team, and intern and resident interviews completed in the first phase, it is clear that in-person simulation will have been more effective at creating the stressful situations that could lead to inappropriate prescribing. Moreover, this approach has been used in numerous prior, unrelated trainings conducted by STRATUS and by the general medicine service.

Providers assigned to the control arm will receive online educational training about other poorly-prescribed medications, including albumin, transfusion, and blood product repletion guidelines. This information will be in the form of electronically-delivered links to information already housed and available at BWH, including reviewing BWH guidelines and literature about transfusion reactions. The interns will be asked to answer several clinical questions about optimal prescribing. Albumin and related products are also high-risk medications often overprescribed on twilight shifts. Receiving education about another high-risk medication will reduce contamination and allow the ability to measure outcomes to other high-risk medications.

Follow-up time for trial evaluation will begin on the day in which the interventions are delivered (planned for Day 2 of their service) and will continue until the end of their coverage block on the twilight team. The interventions in both arms will be delivered on the same day, so there will be equal follow-up time. Upon completion of the trial, we will evaluate outcomes, including prescribing and implementation outcomes, using structured EHR data on the patient-level and a follow-up survey of the interns at 2 weeks after randomization.

We believe that this is a minimal-risk study for several reasons. First, the goal of the study is to improve patient safety, by reducing the prescribing of high-risk medications in older adults in a way that is concordant with well-established clinical guidelines. Second, the intervention itself is a quality-improvement intervention, leveraging resources already available at BWH. Third, all prescribing decisions will be made by the patients' covering providers. Fourth, providers will provide consent for their participation and will not be required to participate. Finally, all patient-level outcomes will be evaluated only through structured EHR data, collected during routine care.

3.3 Study Schema

3.4 Scientific rationale for study design

The use of a randomized trial to evaluate the primary outcome and secondary clinical outcome is scientifically justified, as this design will be able to provide evidence of causality in the effectiveness of the tools on reducing prescribing. An observational study design, by contrast, would not provide the same degree of scientific rigor.

3.5 Justification for intervention

Simulation has increasingly been used to help health care professionals, alone and in teams, practice how they would handle stressful situations such as cardiac arrest or emergent trauma situations in emergency rooms. By extension, leveraging behavioral science principles within simulation to address decisional gaps in System 1 and System 2 thinking holds great promise for reducing for high-risk medications for older adults. Of note, the intervention in this study will be integrated in the intern schedule with minimal impact on workflow. We believe this is a minimal risk intervention overall, as providers could seek to ignore the simulation training and are ultimately responsible for making any prescribing decisions. Patients will not be specifically engaged as part of the trial, as any non-specific attention from the trial protocol in the control arm will undermine the ability to observe the effect of the intervention.

3.6 End-of-study definition

The trial will be completed 1 month after completing randomization. Providers and their eligible patients will be followed until the end of this follow-up date, or until censoring.

3.7 Data sources

Sources of research material, data that will be recorded, when data will be collected

We will use electronic health record (EHR) data to retrospectively identify eligible patients. Data regarding patients' medical history, disease control, medication use, and health care utilization will be obtained from EHR data (Epic). In specific we will extract clinical and financial information from the electronic medical record system (EpicCare), the patient accounting system (Resolute), the patient web portal and the master patient index (Identity). The various tables within these databases are refreshed on a daily, weekly or monthly basis. Data regarding intern scheduling and team assignments will be gathered from Amion®, the residency scheduling system. We will also gather information from provider surveys, one at baseline and one at the end of follow-up.

Linkages to subjects, access to subject identities

Individually-identifiable data are maintained for patient care purposes within the MGB network and are needed to identify patients for evaluation and to monitor care recommendations by providers. Without this linkage, we could not fulfill the study's objectives. To protect the confidentiality of these data, only the minimal necessary research staff will have access to personal identifiers. This will be necessary for linking data and contacting providers. After linkage is completed and study variables are created, all identifiable information will be deleted from the study database. All research staff are properly trained in research management and will be approved by the IRB. All personally identifiable health information will be kept under lock and key.

3.8 Schedule of activities

	Screening (7 days prior to rotation)	Randomization (2 days prior to rotation)	Day 2 of rotation	2-week follow-up
Review of general medical service schedule and outreach to eligible interns	X			
Completion of consent		X		
Completion of baseline questionnaire*		X		
Randomization		X		
Provision of interventions (simulation training and online education)			X	
Adverse event reporting measurement			X	X
Provision of endline (follow-up) questionnaire*				X
EHR and scheduling system data evaluation*				X

***Baseline Questionnaire (Providers):** Demographics (age, sex, race/ethnicity), 6-item State-Trait Anxiety Inventory³², 8-item Physicians' Reaction to Uncertainty Stress from Uncertainty subscale

Endline Questionnaire (Providers): 6-item State-Trait Anxiety Inventory³², 8-item Physicians' Reaction to Uncertainty Stress from Uncertainty subscale, Satisfaction with the interventions

EHR fields:

Baseline: Provider: Prior prescribing of high-risk medications; Eligible patients: Demographics (age, sex, race/ethnicity, insurance status), prior in-hospital use of one of the high-risk medications, admitted on one of the high-risk medications, hospitalization within last 30 days, total no. of home medications;

Follow-up: Prescribing of one of the high-risk medications, prescribing of albumin and other high-risk medications (e.g., opioids), discharge medication orders, administration of the one of the high-risk medications

Scheduling system (Amion®) fields:

Provider: Baseline; Prior inpatient service blocks (i.e., ICU service, ambulatory service), no. of months of internship, characteristics of the rest of the team (i.e., number of residents, seniority of attending, no. of other team members);
Follow-up: Completion of simulation training, no. of days on twilight service

4. Study Population

The study will intervene upon physicians and their older adult patients admitted to the adult inpatient general internal medicine services at BWH and BWFH. We will focus on interns from the “twilight” (i.e., evening) teams as they cover the shifts during which the key high-risk medications of interest (specifically anti-psychotics, benzodiazepines, and sedative hypnotic “Z-drugs”) are typically first initiated and are also the first point of contact for nurses, pharmacists, and other physicians. Given their stage of training and nature of their workflow, they are also most prone to make decisions using System 1 thinking. We plan to exclude patients for the purposes of analysis who were on the relevant high-risk medication of interest prior to admission. For example, patients who were admitted on a benzodiazepine will not be included in the benzodiazepine/sedative hypnotic analysis but will be included in the antipsychotic analysis. Benzodiazepines and sedative hypnotics will be considered interchangeable for this analysis, due to the fact that they have overlapping indications. We will conduct stratified analyses by whether patients by whether they had exposed to one of the high-risk medications during their present admission prior to being under the care of the consenting intern.

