6.2 Outcomes

The primary outcome will be measured on the patient-level as the number of high-risk medication doses prescribed per day to eligible patients beginning on the day the intervention arms are delivered to both arms until the end of follow-up. We will only measure doses ordered by the interns in the study. As described above, we will censor follow-up time on when patients transition from the intern's service, when the intern transitions off the twilight service, discharge, or in-hospital

death. The interventions in both arms will be delivered on the same day, so there will be no immortal time bias. Medications that are written pro re nata (PRN) will be treated the same as standing orders for the primary analysis. If patients are eligible to be measured for multiple medication classes (i.e., antipsychotics and benzodiazepines/sedative hypnotics), we will sum the medication doses across the classes.

In secondary analyses, we will only measure doses that are standing orders (i.e., not PRN doses) and doses that were actually administered to patients. We chose to measure this outcome on the patient-day level, because this would enable the fairest comparison between the arms, given that patients have variable lengths of stay and, as a result, the lengths of time under the interns' care. These data will be collected through structured EHR data from MGB paired with data collected from the scheduling system.

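### In patients eligible for one drug class only, a switch between the two study classes cannot be seen, so the primary effect could be over- or understated by an unknown amount

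*Combined protocol and SAP*

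**What the plan says.** Section 4 (Study Population) sets the entry rule: "We plan to exclude patients for the purposes of analysis who were on the relevant high-risk medication of interest prior to admission". Its example makes the rule class-specific: "patients who were admitted on a benzodiazepine will not be included in the benzodiazepine/sedative hypnotic analysis but will be included in the antipsychotic analysis". There are two counting classes, because "Benzodiazepines and sedative hypnotics will be considered interchangeable for this analysis"; antipsychotics are the other class.

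Section 6.2 says how the primary dose count is built. The summing rule is conditional: "If patients are eligible to be measured for multiple medication classes", then "we will sum the medication doses across the classes". For the secondary versions of the dose outcome, "we will only measure doses that are standing orders (i.e., not PRN doses) and doses that were actually administered to patients"; no different class rule is given for them.

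The spillover endpoint in the Section 2 table is "Number of medication doses prescribed per day to eligible patients assigned to intervention providers versus control providers for opioids, trazodone, and melatonin". Section 6.2 gives the same three drugs as examples and adds albumin and blood products. Neither place mentions the other study class.

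The discharge endpoint in the Section 2 table is "Discharge medication order written for one of the eligible high-risk medications to eligible patients". Section 6.2 describes discharge on any of the study drugs and does not repeat the restriction to eligible ones.

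Section 4.2 gives possible withdrawal as the reason for excluding prior users.

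**The concern.** The primary objective is to find out whether training lowers prescribing of high-risk drugs. That needs a count that does not change when an intern merely swaps one high-risk class for another. For a patient naive to both classes, the sum has this property. For a patient admitted on one class it does not: only half of the possible swap is observed.

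The introduction describes antipsychotics, benzodiazepines and Z-drugs as all being used in hospital for delirium and agitation, so a swap is conceivable. The plan also cares about drug shifting, since it includes a spillover outcome. That outcome, however, leaves out the other class that the training itself targets. If switching differed by arm, the primary estimate would mix a change in total high-risk dosing with a change in which class was ordered, and no planned dose analysis would separate the two.

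**Working it through.** **1. The plan's own patient count.** Section 4.3 gives 36 interns, about 40 patients each, at least 60% older adults and at least 50% naive to either class. 36 × 40 × 0.60 × 0.50 = 432, against the stated minimum of 430 (12 per intern), so the figure reproduces. The 50% is not split into patients naive to one class and patients naive to both, so the single-class share cannot be derived.

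**2. What is counted, from Sections 4 and 6.2 together.**

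| On admission taking | Counted in primary outcome | Not counted |
|---|---|---|
| Neither class | Both classes, summed | – |
| Benzodiazepine or Z-drug | Antipsychotic | Benzodiazepine/Z-drug |
| Antipsychotic | Benzodiazepine/Z-drug | Antipsychotic |

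**3. One patient admitted on a benzodiazepine (hypothetical doses per day).**
- One antipsychotic dose replaced by one extra benzodiazepine dose: counted 1 to 0; both classes 1 to 1. Benefit overstated.
- One extra benzodiazepine dose replaced by one antipsychotic dose: counted 0 to 1; both classes 1 to 1. Benefit understated.
- One extra benzodiazepine dose avoided: counted 0 to 0; both classes 1 to 0. Real benefit not credited.

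**4. Whether another planned analysis catches it.** The standing-order and administered-dose analyses state no different class rule. The strata in Section 4 concern exposure during the present admission, not home use. The examples in Section 7.3.4 do not include home use. The discharge outcome is a yes/no order; even on its broader wording it would not separate a continued home drug from a switch.

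**5. Size, with assumed inputs.** None of these four is in the documents:
- r: fall in each class before replacement (0.30)
- q: share of avoided doses replaced by the other class
- w: share of control-arm counted doses that come from single-class patients (0.10 to 0.40)
- k: in single-class patients, ratio of discretionary excluded-class doses to counted-class doses (0 to 2)

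True fall in total doses = r(1 − q).
Measured fall = r[(1 − w)(1 − q) + w(1 − qk)].
Difference, measured minus true = r·w·q·(1 − k).

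| q | True fall | k = 0, w = 0.10 to 0.40 | k = 1 | k = 2, w = 0.40 |
|---|---|---|---|---|
| 0.25 | 22.5% | 23.25% to 25.5% | 22.5% | 19.5% |
| 0.50 | 15% | 16.5% to 21% | 15% | 9% |
| 1.00 | 0% | 3% to 12% | 0% | −12% (apparent rise) |

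For example, at q = 0.5, w = 0.4, k = 2: 0.30 × [0.6 × 0.5 + 0.4 × (1 − 1)] = 0.09. The sign depends on k: overstatement below 1, none at 1, understatement above 1.

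**6. Precision of an analysis restricted to patients naive to both classes.** With the correlation of 0.2 from Section 7.2, the variance of an intern mean is proportional to 0.2 + 0.8/m.
- Patient-days, m from 36 to an assumed 25: 0.222 to 0.232; √(0.232/0.222) ≈ 1.02, a standard error about 2% larger.
- Patients, m from 12 to an assumed 8: 0.267 to 0.300; √(0.300/0.267) ≈ 1.06, about 6% larger.

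**The case against.** The exclusion is deliberate and has a stated reason, and counting new exposure class by class is a defensible outcome. That stands for continued home doses. It does not explain why new or additional inpatient orders of the home class should be unobserved.

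The switching itself is not shown. Section 5.1 makes all three drug groups training targets, and Section 5.2 trains communication, differential diagnosis and alternative options. Nothing indicates that trained interns would move patients between two classes they were trained to avoid, or would do so more than controls. This stands, and it limits the point to a gap in what the trial can observe.

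Three stronger readings are tempting and are not supported:
- A reader might infer that the bias runs one way, towards apparent benefit. That holds only if single-class patients have no discretionary orders of the excluded class (k = 0 above). With such orders the bias can vanish or reverse.
- A reader might infer that the excluded class counts in no outcome at all. That is safe for inpatient doses under the named outcomes. The discharge outcome as worded in Section 6.2 might capture it, and the spillover drugs there are given only as examples.
- A reader might infer that the plan itself treats the two classes as substitutes. The introduction names a shared use, but Section 4 calls only benzodiazepines and sedative hypnotics interchangeable.

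**Conclusion.** The gap is real and follows from Sections 4 and 6.2 read together, taking the conditional summing rule to mean that a single-class patient contributes doses of one class only. In those patients the trial cannot tell a reduction from a switch between study classes. Patients naive to both classes are not affected.

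Neither the direction nor the size of any bias can be stated. In the illustration with r = 0.30 and q = 0.5, a true 15% fall is measured as 9% to 21%, but every input is assumed and bias requires switching or uncredited reductions that differ by arm. The point does not invalidate the primary analysis. It is a low-cost addition that would make the result of this pilot easier to interpret.

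**What to change.** 1. In Sections 6.2 and 7.3.1, pre-specify as a sensitivity analysis the primary GEE model in patients naive to both classes, where the sum captures any switch. Report its estimate and confidence interval beside the primary result. Do not attach a rule that failure to detect an effect in this smaller set overturns the primary conclusion; non-detection there is not evidence of no effect.

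2. Add to the spillover outcomes, in single-class patients, doses per day of the excluded study class ordered by the intern, compared by arm. Separate new or additional orders from continued home medication where the EHR allows. With 18 interns per arm, chance differences in continued home doses could otherwise hide the signal.

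3. Reconcile the discharge outcome between the Section 2 table and Section 6.2, stating whether an order for the class taken before admission counts.

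Section 3.8 already lists admission on a high-risk drug, prescribing and administration as EHR fields, so no new data source is needed, though separating new from continued orders takes some data work. Otherwise the cost is SAP wording, a few more model runs, and modestly wider intervals in the restricted set (about 2% to 6% under the assumptions in the working).
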